#### **7.1.7. Compensation for participation.**

Participants will not be compensated for their time.

### **7.2 Drugs, Dietary Supplements, Biologics, or Devices.**

216 **7.2.1** Ropivacaine will be the drug used in the stellate ganglion block.

- 217 • Complete names and composition of drugs: Ropivacaine (Naropin).
- 218 • Source of the product: BAMC Pharmacy.
- 219 • Location where study product(s) will be stored: In Pyxis MedStation in the Pain Management Procedure Clinic.
- 220 • Dose range, schedule, and administration route of study product(s): 6.5cc of Ropivacaine HCl 0.5%, one time into
- 221 the stellate ganglion.
- 222 • Detailed description of washout period, if used: not applicable.
- 223 • Duration of study product(s) use: For the duration of the study.
- 224 • Concomitant medications that will be allowed during the study: Only ropivacaine will be used for the stellate
- 225 ganglion block and during the procedure.
- 226 • Any antidotes and treatments available for potential side effects: None.
- 227 • Plan for disposition of unused study product: Per BAMC Pharmacy and Pain Clinic SOP.
- 228 • FDA regulated studies MUST include the following information: The FDA has approved the use of ropivacaine for
- 229 stellate ganglion blocks. We are not seeking a new indication with this research project.

231 **7.2.2** Not applicable, no devices will be used in the conduct of this study.

232 **7.3. Research Interventions/Study Procedures.**

233 **Research Interventions**

234 **Massed Prolonged Exposure.** Prolonged Exposure (PE; Foa, Hembree, & Rothbaum, 2007) is a first-line, empirically  
235 supported cognitive behavioral treatment for PTSD and serves as the foundation for massed PE. Massed PE, delivered  
236 daily over two weeks, utilizes exposure-based interventions to target psychological mechanisms (i.e., experiential and  
237 behavioral avoidance; maladaptive cognitive changes) that are thought to maintain trauma-related symptoms. Ten 90-  
238 minute sessions of massed PE, which has been found to be non-inferior to ten 90-minute spaced PE delivered once or  
239 twice a week over eight weeks, helps minimize military-specific treatment barriers, and decreases treatment dropout rates  
240 (Foa et al, 2018). For the proposed study, each participant will receive ten 90-minute sessions of massed PE over the  
241 course of two weeks. Up to three weeks will be allowed to complete the ten sessions of PE and SGB to accommodate  
242 scheduling constraints. Consistent with the standard spaced PE therapy manual, massed PE includes four primary  
243 treatment components: (1) psychoeducation on common reactions to trauma; (2) relaxation training; (3) in vivo exposure;  
244 and (4) imaginal exposures. In vivo exposure involves approaching avoided situations, people, places, and/or objects that  
245 are realistically safe. With imaginal exposure, participants repeatedly and systematically revisit their trauma memory and  
246 related thoughts and feelings. Participants also will be asked to complete homework, including reviewing treatment  
247 materials, listening to recordings of their imaginal exposure, and completing in vivo exposures. Since massed PE requires  
248 considerable time and effort, the study team will work with the participant to receive a release from duty or work while  
249 participating in the treatment. The preferred method of receiving therapy is face-to-face. However, there may be  
250 circumstances when part or all of the therapy can be administered through telebehavioral/telemedicine health (i. e., phone  
251 session or using a HIPAA-compliant video calling platform). Decisions will be made case-by-case as issues arise for  
252 individuals (such as travel restricted because of a worsening of the pandemic or the need for child care) and in discussion  
253 with the treatment team. Patients who do not have internet access will need to receive treatment in person.

254  
255  
256 Post-treatment Booster Sessions. Massed PE includes three booster sessions that can last up to 1-hour, scheduled for 1  
257 week, 3 weeks, and 7 weeks after the completion of treatment. Booster sessions will be conducted either in person-or by  
258 telebehavioral health as appropriate. Since treatment benefits are derived primarily through the 2-week treatment  
259 program, there will not be an erosion of benefit for participants who do not have the posttreatment booster sessions.

260  
261 **Stellate Ganglion Block (SGB).** Standard procedures for sterilization of the equipment and other universal safety  
262 precautions will be followed. Peripheral intravenous access with a 20-gauge angiocatheter will be obtained as a safety  
263 precaution in the event an intravascular injection occurs during the placement of the SGB requiring intervention.  
264 Participants will be positioned supine on a table and placed into a position that allows optimal visualization of anatomic  
265 landmarks and needle placement. Noninvasive hemodynamic monitors will be used throughout the procedure. A local  
266 anesthetic will be used to numb the skin and needle track. Placement of the SGB will be determined using either  
267 ultrasound or fluoroscopy guidance, depending upon the providers' preference. For the SGB, ropivacaine will be injected  
268 on the right in the anterior or anterolateral edge of the longus colli muscle.

269  
270 **Study Procedures.**

Interested service members will be given a brief description of the study and will be asked to participate in a brief telephone call to determine initial interest in the study. If the individual is still interested, an appointment will be scheduled to meet with research staff to review and document informed consent. This appointment will be held at the UTHSCSA STRONG STAR offices located at [name] or may be completed online or by phone as described in section 7.1.5. As described in the consent, participants on active duty will have the option of having their Command notified by the Research Staff to ensure active duty Service Members are afforded the time to participate in the study. Likewise, retired service members will have the option of having their work supervisor notified to secure their support for participation in the study. Command or work agreement to allow for duty time to participate in this study is not a requirement for study participation. After signing the informed consent document, participants will complete a baseline assessment to determine full eligibility. Structured interviews will be administered by a trained independent evaluator with at least a master’s degree education. As all study procedures are for screening or research purposes, the item responses will be maintained in the participant’s research file and not be entered into the participant’s electronic medical record.

During the course of the assessment, if a participant’s symptom reports indicate that he or she is at high risk for suicidality according to the “STRONG STAR Suicide\_Risk\_Assessment\_and\_Risk-Crisis\_Management” SOP, risk management procedures outlined in this SOP will be followed. If the research team feels that hospitalization should be considered, the participant’s primary care provider or unit will be contacted to escort the individual to the ED. If a participant reports experiencing psychotic or mania symptoms, or reports dangerous amounts of alcohol and/or substance use, additional assessment by a licensed provider for consideration of referral for clinical care and for screening participants out of the study will be conducted. If a participant is determined to be ineligible for the study for any reason, a referral back to the referring provider or the patient’s primary care provider for clinical follow-up will be made.

Once it has been determined that individuals meet the inclusion and exclusion criteria, participants will work with the research staff to schedule treatment and, if requested, secure a release from duty from their command or work to participate in the two-week treatment. Massed PE will be conducted by doctoral-level therapists at the UTHSCSA STRONG STAR offices. Participants will meet with their providers for individual, 90-minute sessions. They will then be asked to complete out-of-session treatment assignments throughout the rest of the day. Between the individual therapy session and out-of-session treatment assignments, participants will engage in approximately four to six hours of treatment per day, Monday through Friday, for two weeks. The stellate ganglion block injection will be administered between the first and second massed PE session at the BAMC Pain Clinic by qualified medical personnel supervised by MAJ [name] [name]. The BAMC SOP for the placement of a stellate ganglion block will be followed. A research nurse will be in attendance during the procedure and will recover the participant for at least 1 hour following the procedure.

During PE treatment, participants will complete interim assessments of their PTSD symptoms, mood symptoms, trauma-related cognitions, and suicidal ideation preceding sessions 6 and 10. This abbreviated assessment battery will include the PTSD Checklist for the DSM-5, Patient Health Questionnaire-9, Depressive Symptom Index – Suicidality Subscale, and Posttraumatic Cognitions Inventory and should take less than 15 minutes to complete. The full assessment battery outlined in the measure section will be re-administered one- and three-months following the completion of treatment by an independent evaluator. These assessments may occur in person at the UTHSCSA STRONG STAR offices or online/by phone as needed to accommodate participant scheduling and circumstances.

In order to examine the safety of the stellate ganglion block in combination with massed PE for the treatment of PTSD, adverse event monitoring will be conducted throughout the treatment phase, at each interim assessment, and again at the one-month posttreatment and three-month follow-up assessments. STRONG STAR has well established standard operating procedures for adverse event monitoring. An adverse event that leads to hospitalization will be considered a serious adverse event (SAE), and adverse events that are unexpected and increase risk to participants will be considered an Unanticipated Problems Involving Risk to Subjects or Others (UPIRSO). SAEs and UPIRSOs will be promptly reported to the IRB. The categorization and relatedness of each potential adverse event will be adjudicated by the study team during weekly calls.

Study Procedures	Base Line	PE Day 1	SGB Txt between Txt PE Days 1& 2	PE Days 2-5	Interim Assess Day 6	PE Days 6-9	Interim Assess Day 10	PE Day 10	1wk Post txt	3wk Post txt	1M F/U	7wk Post txt	3M F/U
Phone Discussion													
Informed Consent	R												

Study Procedures	Base Line	PE Day 1	SGB Txt between Txt PE Days 1& 2	PE Days 2-5	Interim Assess Day 6	PE Days 6-9	Interim Assess Day 10	PE Day 10	1wk Post txt	3wk Post txt	1M F/U	7wk Post txt	3M F/U
Demographics and Military Service Characteristics Form	S,R												
Life Events Checklist for the DSM-5	S,R										R		R
Deployment Risk and Resilience Inventory-2	S,R												
Mini International Neuropsychiatric Interview (MINI 7.0) Psychosis and Mania modules	S												
Health Questionnaire	R										R		R
Health Questionnaire-Supplemental for SGB	S												
Self-Injurious Thoughts and Behaviors Interview short form	S,R										R		R
Depressive Symptom Index – Suicidality Subscale	S,R				R		R		R	R	R	R	R
Clinician-Administered PTSD Scale for the DSM-5	S,R										R		R
PTSD Checklist for the DSM-5	R				R		R		R	R	R	R	R
Patient Health Questionnaire-9	S,R				R		R		R	R	R	R	R
Generalized Anxiety Disorder-7	R										R		R
Brief Inventory of Psychosocial Functioning	R										R		R
Veterans RAND 12-Item Short Form Health Survey	R										R		R
Alcohol Use Disorders Identification Test	S,R										R		R
Insomnia Severity Index	R										R		R
Posttraumatic Cognitions Inventory	R				R		R		R	R	R	R	R
Credibility and Expectancy Questionnaire for PE			R								R		R
Credibility and Expectancy Questionnaire for SGB			R								R		R
Massed Prolonged Exposure (PE)		R		R		R		R					

Study Procedures	Base Line	PE Day 1	SGB Txt between Txt PE Days 1& 2	PE Days 2-5	Interim Assess Day 6	PE Days 6-9	Interim Assess Day 10	PE Day 10	1wk Post txt	3wk Post txt	1M F/U	7wk Post txt	3M F/U
Ultrasound or Fluoroscopy (for SGB placement guidance)			R										
Stellate Ganglion Block (SGB)			R										
Adverse Event Monitoring		R	R	R	R	R	R	R	R	R	R	R	R
Urine Pregnancy Test	S												
Booster Sessions									R	R		R	

Key: R = administered for research purposes, S = administered for screening purposes

**7.3.1 Collection of Human Biological Specimens.** Urine pregnancy tests will be conducted at baseline.

**7.3.1.1 Laboratory evaluations and special precautions.** Urine pregnancy test will be conducted at baseline and the remaining sample will be discarded. Universal precautions will be followed when collecting and testing all urine samples.

**7.3.1.2 Specimen storage.** Not applicable

### 7.3.2 Data Collection.

A comprehensive list of assessments is included in the Section 7.3 table. The data collected in the study will be coded using an assigned number. Hard copies of data collected during the study will securely stored in locked cabinets at the STRONG STAR offices. Data will be entered into the STRONG STAR database on a secure UTHSCSA server (physically located at the Advanced Data Center), by member of the research team. Electronic data will be stored, managed, and analyzed by the STRONG STAR – Data and Statistics Core staff of the STRONG STAR consortium. Every member of the Research Team will be trained and monitored about how to handle and protect both medical and research records. Furthermore, the Research Team strictly controls access to study data.

**7.3.3. Human Biological Specimens/Tissue/Data Banking.** Not applicable

## 7.4 Statistical Consideration

**7.4.1 Sample Size Estimation.** This study is a pilot investigation. Consequently, a power analysis was not conducted.

Estimate Required Sample Size	12
Screened Out/Excluded	12
Estimate Participant Drop Out / Withdrawal	3
Total Enrollment Requirement	27

### 7.4.2 Primary (i.e., primary outcome variables) and secondary endpoints.

The primary aim of this pilot is to explore the potential treatment effectiveness and safety of a stellate ganglion block combined with Massed Prolonged Exposure in reducing PTSD symptoms in active duty and retired service members. Therefore, the primary outcome variables include the CAPS-5 severity score, the PCL-5, and adverse event monitoring. Secondary endpoints include associated psychopathology (severity scores on measures of depression, general anxiety, disability, and PTSD-related cognitions).

### 7.4.3 Data analysis.

Prior to statistical analyses, the data will be carefully inspected to identify such problems as unusual distributions, the desirability of transformations (e.g., logarithmic is often useful), missing data, and outliers. Data are also screened to identify potentially important covariates, i.e., variables (e.g., age) that are not of primary interest in the hypotheses but that

360 relate to the outcome measures (including such variables as covariates increases power and reduces bias).The primary  
361 software for statistical analyses is the SAS statistical system, that is widely available and well known. Our current version  
362 is SAS 9.4. We also have specialized software, including Stata 14, Mplus 8.2, and SPSS 25.

363  
364 The proposed study is in preparation for a larger clinical trial, with the primary goals of the pilot study being to  
365 demonstrate feasibility through evaluating recruitment, retention, and adverse events, and to estimate the magnitude of  
366 potential impact on selected outcomes. A total of 12 participants with PTSD to receive a combination treatment of Massed  
367 Prolonged Exposure with a stellate ganglion block will be included in the analysis. Assessments will be done at three time  
368 points (baseline, one- and three-months following the completion of treatment). Statistical analyses will be intent to treat,  
369 using all data from participants regardless of the extent of participation. We are requesting to consent up to 27  
370 participants to include 12 participants for analysis.

371  
372 The primary aim of this project is to evaluate the effectiveness and safety of a stellate ganglion block combined with  
373 Massed Prolonged Exposure for the treatment of PTSD in active duty and retired military service members. Tests of the  
374 descriptive hypotheses will involve calculation of the relevant proportions with 95% confidence limits based on PTSD  
375 diagnosis, PTSD symptom severity, and adverse events over the course of therapy, and dropout.

### 376 377 **7.7 Confidentiality.**

378 All Prolonged Exposure sessions and interview assessments will be delivered in private offices at the STRONG STAR Clinic  
379 at the UTHSCSA. The stellate ganglion block will be administered in Pain Clinic at the Brooke Army Medical Center following  
380 standard operating procedures for patient safety and confidentiality. Data will be stored by an assigned participant code  
381 number so that data records can be viewed by password-authenticated, authorized investigators and Consortium personnel.  
382 Digital audio recordings of assessments and PE sessions will be labeled with the participant's study id number and saved on  
383 a secure password protected server. Those recordings, to be reviewed for fidelity to ensure that the treatment is being  
384 delivered in accordance with the treatment manual, will be viewed on a secure, password protected server. There is no option  
385 for the reviewers to download or otherwise save the recordings to their computers. Every member of the Research Team will  
386 be trained and monitored about how to handle and protect both medical and research records. The recording will be deleted  
387 from the recorder after it has been saved to the secure password protected server. In the circumstance that an audio  
388 recording cannot be immediately saved (e.g., network or electrical outage, computer unavailable, etc.), the recording device  
389 will be placed in a locked file cabinet in the STRONG STAR Clinic offices. Study staff will be responsible to upload the  
390 recordings as soon as possible and then deleting the recording from the recorder. Only authorized study staff, and members  
391 of the STRONG STAR Biostatistics and Data Management Core staff will have access to either the raw data or electronic  
392 study data.

393  
394 **7.7.1 Certificate of Confidentiality.** We are not seeking a Certificate of Confidentiality.

### 395 396 **7.7.2. Data Protection.**

397 Data will be coded using an assigned number. Data collected during treatment will be placed into a locked filing cabinet  
398 and stored securely in a locked room by a STRONG STAR staff member. Files will be kept securely at the University of  
399 Texas Health Science Center (UTHSCSA) STRONG STAR offices in San Antonio. The STRONG STAR data server is  
400 physically located at the Advanced Data Center (ADC) has 24x7 onsite security, card key, biometric access controls and  
401 video surveillance. University of Texas Health Science Center at San Antonio (UTHSCSA) ADC facility also maintains  
402 Gen 2 firewall devices to protect and prohibit any unauthorized access to UTHSCSA data. All UTHSCSA network devices  
403 are monitored by state of the art monitoring applications that include configuration audit, management, and availability  
404 24x7. Every member of the Research Team will be trained and monitored about how to handle and protect both medical  
405 and research records. Furthermore, the Research Team strictly controls access to study data. The local study site will  
406 maintain a list of assignment numbers for the purpose of linking subsequent research materials.

407  
408 A Data Safety and Monitoring Plan (DSMP) has been developed in accordance with the National Institutes of Health  
409 Office of Human Research Protection to assure the appropriate clinical safety monitoring of study subjects participating in  
410 this study.

### 411 412 **7.7.3. Long Term Data Storage.**

413 A *STRONG STAR Repository* has been approved by both the UTHSCSA (HSC20100475H) IRB to enable the STRONG  
414 STAR Consortium to store specimens and data for future use. The STRONG STAR Repository will create a large  
415 comprehensive database of information, biological specimens and neuroimages related to the identification, assessment, and  
416 treatment of PTSD in our active duty and retired veterans of conflicts following 9-11. All information entered into the STRONG

STAR Repository will be extracted from primary datasets collected as part of IRB-approved studies, including this study, being conducted and /or supported by the projects of the STRONG STAR Consortium. These study databases will be established and maintained by the Biostatistics and Data Management Core of the STRONG STAR Consortium. A unique, sequential alpha-numeric STRONG STAR ID will be assigned to each participant at the time of recruitment into this study. However, all Repository data will be identified with a different code number that can be cross linked to the original study code only through records maintained by the STRONG STAR Biostatistics and Data Management Core. Data, biological specimens and images will constitute the STRONG STAR PTSD Repository. Participation in the repository will be completely voluntary and entirely optional which means that a potential participant's willingness to participate in the repository has no influence upon their eligibility to participate in the primary STRONG STAR study they have either already enrolled in or are considering enrolling in. At the conclusion of this study, participants who signed the consent to have their specimens and data placed in the STRONG STAR Repository will be maintained under the IRB-approved Repository protocol. Biological specimens and information from study participants who declined participation in the STRONG STAR Repository will be permanently de-identified (i. e., all PHI will be deleted from the study data bases) and the de-identified blood and information placed in the STRONG STAR Repository for future use.

## **8.0 RISKS/BENEFITS ASSESSMENT**

### **8.1 Risks.**

#### Likely, but Not Serious Risks

Potential risks associated with the assessments and PE can include temporary increase in relationship distress, becoming emotionally upset or experiencing an initial increase of PTSD symptoms due to the consideration of traumatic events. Studies with PE suggest that a small minority experience an increase in symptoms of PTSD after the initiation of imaginal exposure exercises and for this minority, the distress and increased symptoms are temporary, are not predictive of poor outcome, and are not associated with increased likelihood of dropout (Foa et al., 2002).

Potential risks associated with the stellate ganglion block can include a temporary change in skin temperature; temporary hoarseness, voice changes or loss of voice; or Horner's Syndrome.

Potential risks related to ropivacain used in the stellate ganglion block can include signs of an allergic reaction (hives or red skin rash; dizziness; sneezing; difficulty breathing; nausea or vomiting; sweating; swelling of your face, lips, tongue, or throat; gastrointestinal distress; pain (headache, back pain); skin (itching); numbness or tingly feeling; fever; genital-urinary (problems with urination or sexual function).

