#### Rare, but Serious Risks

With the handling of medical and research records there is always the possibility of a breach of confidentiality. However, every effort is made to protect the privacy of participants. Every member of the Research Team is carefully trained and monitored about how to store, handle, and protect participant records.

Rare but more serious risks associated with the stellate ganglion block include bleeding from a broken blood vessel that results in a hematoma; injury to the nerves around the injection site; injury to the esophagus; pneumothorax; spinal cord trauma; infection of the tissues of the neck, nerves, bone or disc material in the area of the injection or IV placement; incomplete recovery of normal function.

Rare but more serious risks related to ropivacain used in the stellate ganglion block include feeling anxious, restless, confused, or like you might pass out; problems with speech or vision; ringing in the ears, metallic taste, numbness or tingling around the mouth, or tremors; seizure (convulsions); weak or shallow breathing; slow heart rate, weak pulse or fast heart rate, gasping, feeling unusually hot.

Rare but more serious risks if fluoroscopy is used for a prolonged time to guide the placement of the block are reddening of the skin, a very slight increase in the chance of contracting cancer, and a potential risk to an unborn embryo/fetus should a woman undergoing fluoroscopy be pregnant. Normally fluoroscopy will be used for less than one minute.

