#### **9.2 Reporting Unanticipated Problems Involving Risks to Subjects or Others, Serious Adverse Events and Deaths to the IRB of Record.**

All adverse events, unanticipated problems involving risk to subjects or others, and deviations will be reported to the Institutional Review Board (IRB) in accordance with current IRB policy. UPIRSOs and recurrent non-compliance with study procedures will be reported promptly to the IRB. All adverse events that do not meet the UPIRSO criteria and deviations that are not non-compliance will be summarized at Continuing Review per the IRB of record's policy.

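### Severe allergic signs are listed as likely and not serious, and the stated SAE criterion and section 9.2 leave some grave but expected events without a written prompt route to the IRB

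*Combined protocol and SAP*

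**What the plan says.** **Risk listing, section 8.1.** The first group of risks is headed "Likely, but Not Serious Risks". Its ropivacaine paragraph introduces signs of an allergic reaction and includes "difficulty breathing; nausea or vomiting; sweating; swelling of your face, lips, tongue, or throat". The next group, Rare, but Serious Risks, has its own ropivacaine paragraph. That paragraph includes "weak or shallow breathing; slow heart rate, weak pulse or fast heart rate, gasping", together with seizure, tremor, metallic taste and ringing in the ears. It does not mention allergic reaction.

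**Definitions and reporting, section 7.3 (Study Procedures).** Seriousness is set by one criterion: "An adverse event that leads to hospitalization will be considered a serious adverse event (SAE"). The second category is defined by expectedness and risk: "adverse events that are unexpected and increase risk to participants will be considered an Unanticipated Problems Involving Risk to Subjects or Others". Both have the same route: "SAEs and UPIRSOs will be promptly reported to the IRB".

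**Reporting, section 9.2.** The heading covers "Serious Adverse Events and Deaths to the IRB of Record". The opening sentence says that adverse events, unanticipated problems and deviations "will be reported to the Institutional Review Board (IRB) in accordance with current IRB policy". The body then names UPIRSOs and recurrent non-compliance for prompt reporting. Adverse events that are not UPIRSOs are to be summarized at Continuing Review, again subject to the IRB of record's policy. SAEs and deaths appear in the heading but are given no route of their own in the body.

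**Related text.** Section 9.1 refers adverse event monitoring to a STRONG STAR SOP and to the IRB's policies. Section 7.7.2 says that a Data Safety and Monitoring Plan exists. Section 7.4.2 makes adverse event monitoring one of the primary outcomes.

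**The concern.** There are two separate points.

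The first is a label. Swelling of the throat with trouble breathing is a medical emergency, and a risk assessment should not tell its readers that it is both likely and not serious. Because the serious list has no allergic entry, nothing elsewhere in 8.1 corrects the impression.

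The second is the written path by which the IRB learns of a grave event. Hospitalization is a narrow test of seriousness. Section 8.1 itself directs participants with urgent problems to the Emergency Department, so a dangerous reaction could be treated there without admission. It also names suicide as a risk of PTSD in and out of treatment, and a death need not follow an admission. If such an event is also judged expected, it falls outside both categories that 7.3 sends promptly to the IRB.

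The pilot is meant to establish the safety of the combination, so the rules for classifying and reporting grave events should be complete in the protocol itself. What is at stake is the speed of IRB notice and the consistency of the risk assessment. The event would still be recorded as an adverse event.

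**Working it through.** The plan states no figure on this point and no arithmetic applies. The check sets the texts side by side and follows four kinds of event through them.

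**Label.** The ropivacaine sentence in the first risk group says only what the risks can include and gives no frequency. The words likely and not serious therefore come from the group heading. The parenthesis opened after the mention of allergic reaction is never closed, so it is unclear where the allergic signs end. The two airway items fall under the heading on any reading. Milder entries in the same sentence, such as itching and nausea, are reasonably placed there. The misplaced items are the severe allergic signs.

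**Reporting.** The inputs are the SAE and UPIRSO definitions and the prompt rule in 7.3, and the prompt and Continuing Review rules in the body of 9.2.

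1. *Unexpected, risk-increasing event that leads to admission.* It is both an SAE and a UPIRSO. Section 7.3: prompt. Section 9.2: prompt. No gap.
2. *Expected event that leads to admission.* It is an SAE, but not a UPIRSO, because a UPIRSO must be unexpected. Section 7.3: prompt. Section 9.2 read alone: Continuing Review summary. Staff who follow both sections report promptly and summarize later. Staff who work from 9.2 alone find no prompt instruction.
3. *Unexpected, risk-increasing event that is fatal or life-threatening, without admission.* It does not meet the stated SAE criterion, but it is a UPIRSO. Both sections: prompt. No gap.
4. *Expected event that is fatal or life-threatening, without admission.* It does not meet the stated SAE criterion and is not a UPIRSO. Section 7.3: no prompt instruction. Section 9.2: Continuing Review summary, subject to IRB policy. Neither section states a prompt route.

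Case 2 is a missing cross-reference. Case 4 is a gap in the stated definition, and joining the two sections does not close it. Cases 1 and 3 show that the issue is confined to events judged expected.

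**The case against.** The strongest reply is that the two sections do not contradict each other. Section 9.2 does not say that only UPIRSOs are reported promptly, and it does not exempt SAEs from 7.3. An expected SAE can be reported promptly under 7.3 and summarized again under 9.2. This stands: a reader might infer a conflict, but the text supports only an omission in 9.2.

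The second reply is that 9.1, the opening of 9.2 and the Continuing Review sentence all defer to IRB policy, 9.1 also to an SOP, and that a monitoring plan exists. Any of these may already require prompt notice of deaths and life-threatening events. This also stands, as a limit on how firmly the reporting point can be put.

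Third, participants are well protected: known allergy to local anesthetics is excluded (7.1.3), intravenous access and hemodynamic monitoring are in place, a nurse stays for at least 1 hour, and events are adjudicated weekly (7.3). These measures lower the clinical risk. They do not change the label or supply a reporting route.

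Four stronger readings are tempting and are not supported:

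- *The protocol ranks breathing compromise from one drug as both serious and not serious.* The breathing signs in the serious list sit with seizure, tremor and metallic taste and are not presented as allergy. They are different symptom groups.
- *Listing in 8.1 makes an allergic reaction expected and so delays its report.* No text ties expectedness to that list. The two points are independent.
- *The research monitor would not hear of an event that is not a UPIRSO.* The monitor's duties in 8.1 are given as examples; they also include overseeing interventions and data collection, and the monitor may interview participants.
- *A number of further injections would be given before the IRB knew.* The Continuing Review interval is not given, two participants per month is an anticipated pace and not a cap, and no event rate is stated. No such count can be defended.

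**Conclusion.** Both points hold, and both are minor.

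The label point rests on the text alone: severe allergic signs stand under a heading that calls them likely and not serious, and the serious list omits allergic reaction.

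The reporting point is narrower. Section 9.2 read alone gives an expected SAE no prompt route, although 7.3 does. A fatal or life-threatening event without admission does not meet the stated SAE criterion and, if judged expected, has no prompt route stated in either section. This takes the hospitalization criterion literally and assumes that the IRB policy, SOP and monitoring plan do not add to it. They are not in the documents and may settle the matter, so confidence is moderate.

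No probability of harm can be given, because the documents state no event rate. The sample size and the planned proportions with 95% confidence limits are unaffected. The point is still worth acting on, because safety is a primary outcome and a few words close the gap.

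**What to change.** - **Section 8.1:** move severe allergic reaction, naming difficulty in breathing and swelling of the face, mouth or throat, to the ropivacaine paragraph of Rare, but Serious Risks. Leave the minor skin and stomach symptoms where they are.
- **Section 7.3:** define an SAE as an event that is fatal, is life-threatening, or leads to hospitalization.
- **Section 9.2:** state that every SAE as defined in 7.3 is reported promptly to the IRB whether or not it was expected. If the IRB policy, the SOP or the monitoring plan already requires this, cite the governing clause instead.

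The cost is three short wording changes and at most a few extra prompt reports. No endpoint, dose, visit or analysis changes.
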